## **Data Collection**

### *Stool microbiome:*

Stool will be obtained at home by the patient prior to colonoscopy and bowel prep, after surgery but prior to FOLFOX treatment, and on the 2nd day after TD15, TD71 and TD128. The patient will obtain stool samples according to the directions provided in the kit (**Comprehensive Stool Kit FED EX Ready**). Subjects will collect stool in the stool hat after first voiding urine, and will use the collection vial with scoop to obtain a stool sample. The patient will then put the labeled stool collection vial into the biohazard bag and put the bag into the shipping box along with three frozen ice packs. The patient will either drop the stool samples in the box with ice packs to their treatment hospital or call for FedEx pick up at home. The samples will be received at the [name] lab at Baylor University (BSL2) and will be shipped to [name] at the Alkek Metagenomics and Microbiome Research Center in Houston, TX at Baylor College of Medicine. This will occur for each time point in the study for stool collection.

**DNA extraction:** For fresh extraction, samples will arrive in PowerBead tubes provided. For banked approach samples, initial thawing on ice with subsequent sample addition to PowerBead tubes. Nucleic acid is freed with extensive vortexing, and subsequent transfer of supernatant to collection tubes for extraction using filter-based centrifugation in a modified MoBio protocol (HMP protocol).

**Sequencing overview:** The predominant metagenomics sequencing strategy will focus on 16S rDNA MiSeq sequencing using the V4 region primers. This takes advantage of existing and fully functional technology and pipelines with proven reproducibility and quality reads in a self-sampled population studies. In addition to bacteria, archaea will be surveyed by the addition of different primer sets to amplify archaeal 16S rDNA sequences, and fungi will be identified by 18S rRNA gene/ITS-based sequencing. Sequencing of the bacterial 16S rRNA gene targets will be performed in collaboration with

the existing HMP Genome Sequencing Centers (Baylor College of Medicine). Proper positive and negative controls will be in place to control for contamination.

**Bioinformatics overview:** Read data will be filtered and analyzed using our validated 16S rRNA analysis pipeline in the [name] lab, which is housed on the Kodiak server at Baylor University. Sequencing analysis will be conducted using the QIIME bioinformatics pipeline and operational taxonomic unit (OTU) classification will be obtained. Specifically, 16S rRNA gene sequence data will be conducted by first demultiplexing fastq files generated by the MiSeq platform first screened for length and quality using QIIME. Reads containing more than five consecutive low quality base calls (Phred < Q20) will be truncated at the beginning of the low-quality region. Passing sequences will be required to have high quality base calls ( $\geq$  Phred Q20) along with a minimum of 75% of the read length to be included. After primer removal, final sequences containing ambiguous bases (Ns) or lengths less than 150bp will be removed. High quality sequences will be screened for spurious PhiX contaminant using BLASTN with a word size of 16. Reads will be assessed for chimeras using USEARCH61 (de novo mode, 97% identity threshold for clustering). Non-chimeric sequences will be screened for contaminant chloroplast and mitochondria using the RDP naïve Bayesian classifier, as well as non-specific human genome contaminant using Bowtie2 against the UCSC hg19 reference sequence. Finally, sequences will be evaluated for residual contaminants using BLASTN searches of the GreenGenes database (v13.5). High-quality passing sequences will subsequently be clustered into operational taxonomic units using the open-reference operational taxonomic unit (OTU) picking methodology implemented within QIIME using default parameters and the GreenGenes database (99% OTUs) supplemented by reference sequences from the SILVA database (v111). Prior to downstream diversity analyses, taxa with <5% abundance in all samples will be dropped from downstream analysis. Alpha diversity estimators and beta-diversity metrics will be computed in QIIME with differential abundance analyses performed in R. Mann-Whitney tests corrected for multiple testing (Benjamini–Hochberg (FDR)) will be used to conduct initial comparisons between time points.

*Metabolite Analysis:*

The stool samples collected and stored in 95% ethanol will undergo metabolite analysis (using the iHMP protocol; <https://ibdmdb.org/cb/browser/Clinical%20Protocol>) in the laboratory of [name] (Collaborator, BU) using high-performance liquid chromatography for SCFAs and indoles according to previous methods, as well as, putative metabolites identified from the PIPHILLIN algorithm. We will use a chromatographic approach based on Tuomola et al., to quantify these indoles and their other analogs. Stool samples will also be analyzed for SCFA (acetic acid, propionic acid, butyric acid, isobutyric acid, valeric acid, and isovaleric acid) with liquid chromatography associated to mass spectrometry.

*Circulating Cytokines:*

Levels of circulating cytokines at baseline (prior to surgery), prior to FOLFOX (treatment naive), and during treatment will be captured at the same time as regular blood draws to minimize patient risk and discomfort. Clinical staff will be provided with labels for each patient attached to their chart to apply to the tubes at the time of blood draw. All clinical specimens will be labeled with the participant code, date of sample acquisition and type of sample (e.g. blood 01), then placed in the clinical laboratory refrigerator within 2h after collection to maintain storage at 4°C until processing serum. Serum samples will be centrifuged and immediately stored at -80°C until shipped to the [name] lab in batch for processing. Cytokine measures will be conducted using the Luminex technology.

*Tissue Biofilm Quantification:*

Invasive biofilms (>200 micrometers) will be assessed after CRC and paired normal tissue is collected from enrolled patients undergoing surgery at Baylor Scott and White. The pathologist will use aseptic techniques to process the tissues immediately after tissue collection. All tissue not needed for pathologic diagnosis will be rapidly preserved in formalin, Carnoy's solution and RNAlater for analysis. For patients in this study, two bowel preparations will be used and recorded (mechanical bowel preparation [MiralaxTM], or Fleet Phospo-sodaTM enema). Pre-operative intravenous antibiotics are administered in all

cases (cefotetan or clindamycin/gentamycin). Oligonucleotide probes will be synthesized and conjugated at the 5' end to the fluorophore Cy3, Alexa 405, Alexa 488, Oregon Green 514, Alexa 514, Alexa 555, Rhodamine Red X, Texas Red X, Alexa 633 or Alexa 647 (Invitrogen Life Technologies). Twelve probes will be applied to 5  $\mu$ m thick Carnoy's solution-fixed paraffin-embedded tissue sections. All samples collected will also be stained with the Eub338 universal bacterial probe to detect all bacteria present on the sample. Successive sections will be stained with Periodic acid Schiff (PAS) to confirm mucus presence and preservation. Samples that are determined to have a bacterial presence by universal probe will be analyzed using group and species specific probes. Slides will be de-waxed following standard procedures. Probes will be applied to slides at a concentration of 2 pmol/ul in prewarmed hybridization buffer (900 mM NaCl, 20 mM Tris pH 7.5, 0.01% SDS, 20% formamide). Slides will be incubated at 46°C in a humid chamber for 2 hours, and washed at 48°C for 15 minutes in wash buffer (215 mM NaCl, 20 mM Tris pH 7.5, 5 mM EDTA). Slides will be dipped in water, then in 100% ethanol, air-dried, and coverslips mounted using ProLong Gold antifade reagent (Life Technologies). Biofilm bacterial density and depth will be measured using slides hybridized with the universal bacterial probe, Eub338, and imaged at 1000x magnification with a Nikon E800 microscope and Nikon NIS elements viewing software.

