### **Sample Population:**

Inclusion/exclusion criteria – the study population will be derived from the two participating BSW hospital systems (Waco and Temple, TX) and will be selected to participate in the study on the basis of the following criteria (inclusion): Age  $>18$  and  $\leq 79$  years, written informed consent, ability to perform informed consent, FOLFOX treatment and Stage II/III colon cancer diagnosis. To ensure fitness for recurrence detection and anti-cancer therapy, the age was restricted to  $>18$  so as not to include minors, and  $\leq 79$  years based on life expectancy with colon cancer diagnosis. Individuals will be excluded from participating if any of the following criteria are met: not diagnosed with stage II or III colon cancer, pregnancy, Lynch syndrome or FAP diagnosis, inability or refusal to perform informed consent, inability to comply with the follow-up program, history of previous colon cancer diagnosis, previous treatment with antibiotics in the last month, previous bowel resection.

Sample size - Based on current data from BSW, the recurrence rate for stage II/III colon cancer is 20%, with a 10% 5-year survival rate for stage IV colon cancer. Given our study design, we conducted power calculations for each group. To meet the number required to detect chemotherapy induced diarrhea and mucositis associated with microbial and metabolite abundance, we need to collect at least 560 stool samples from 112 people (Observational Study). To meet the power requirements for detection of differentially abundant microbes and metabolites associated with chemotherapy-induced CID we estimate needing at least 100 stage II/III patients. The specific power calculation for these groups are provided below.

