### Taxonomic differential abundance analysis

Power calculations for differential abundance analysis in human microbiome studies can be challenging, as there is limited data with highly consistent sample preparation available and uncertainty in the overall distribution of bacterial taxa throughout the human population. Recently, a CRC stool-based microbiome study of a large cohort was performed by Baxter and colleagues. This publicly available data serves as a potential resource for power-analyses by allowing for empirical calculation of the expected variability of taxa in both healthy and CRC-associated gut microbiomes.

We obtained the raw 16S rRNA sequence data from the Baxter study including patients with CRC (n=120) and healthy controls (n=172). After preprocessing and subsampling high-quality reads to an equivalent depth of 10,000 per sample, we identified 92 genus-level groups that each represented (on average) at least 0.25% of sequences from the CRC or healthy patient groups. We then computed the corresponding variance in relative abundance for each of these 92 taxa, and used the empirical values to perform a comprehensive power-analysis.

As expected, increased statistical power was found with higher abundance genera, so here we focus on power results for organisms reflecting an average of 0.25-1.0% of 16S sequences in the gut microbiome because detecting differences in these rare taxa may be critical to our study. Among the genera found at this low level, if we assume equal variance in two normally-distributed populations and require a significance level of  $\alpha=0.05$ , we expect that with a comparison of 40 vs 100 individuals, we will be able to detect a relative increase of 200% (e.g. 0.5% mean abundance increased to 1.5%), with a statistical power of 92.3% (*pwr.t2n.test* in R).

Considering the genera with average frequency  $>1\%$ , we estimate that with a 40 vs 100 sample comparison, we will be able to detect a relative increase of 200% (e.g. 1% mean abundance increased to 3%, or 2% mean abundance increased to 6%), with an expected statistical power of 99.6%.

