#### **4.4 Data Analysis.**

Classification of taxa associated with side effects or severity: Recently, in an animal model of colon tumorigenesis (AOM/DSS), investigators used the initial microbial community structure (16s rRNA sequencing) to predict tumor burden after exposure to various antibiotics during colon carcinogenesis. In order to conduct a similar analysis and reduce data dimensionality, we will first perform cluster modeling using Dirichlet multinomial mixtures (Holmes et al. 2012) to identify microbial clusters (community state types). To determine which taxa or taxonomic cluster are the best predictors of treatment side effects (CID, mucositis) and severity (stage 3-4), we will conduct 10-fold cross-validation using the RandomForest package (Version 3.6.4) in R (R-studio, Version 0.98.1091; Boston, MA). Specifically, 5,000 trees will be used and the parameter mtry will be set at 100. The taxa with the highest importance scores will be used for further analysis. This procedure will be tested by splitting the data into test and training sets, then running Random Forest using the same procedure described above on the training dataset and comparing the predictive accuracy of the top taxa (based on importance scores) in the test set. Based on this 10-fold cross-validation, we will be able to calculate sensitivity and specificity. These top taxa will then be used to generate receiver operator curves (ROC) and calculate area under the curve (AUC). Each microbial cluster or taxa will undergo independent logistic regression testing to calculate area under the ROC curve using Stata (v13). The command roccomp will be used to compare statistical difference between AUCs and determine the best combination of taxa for classification of CID or mucositis and for severity.

Microbiome-Diet Analysis: To evaluate the impact of diet on the stool and tissue microbiome, we will use the dietary analysis generated from the ASA24 and DHQIII, which includes the Healthy Eating Index (HEI). Prior to analysis, we will conduct normality testing for each variable using Shapiro-Wilk test. For any variables that do not pass, a logarithm transformation will be performed. In order to identify any potentially important diet or nutrient-microbiome associations, we will conduct correlation analysis between dietary macronutrients (carbohydrates, fats, proteins) or micronutrients (vitamins and minerals)

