and microbial clusters (community state types) at baseline using Kruskall-Wallis, and for individual taxa using Pairwise Spearman correlations. We will use PERMANOVA for comparing beta-diversity (weighted UniFrac distances) at baseline by levels of macro- and micronutrients. DESeq2, Kruskall-Wallis and Mann-Whitney tests will be conducted to identify significant differences in tissue and stool taxa or microbial clusters according HEI scores at baseline. The Benjamini and Hochberg false discovery rate (FDR) will be used to correct for multiple testing. Taxa or microbial clusters found to be significantly differentially abundant between treatment time points and baseline will be used to conduct 'random forest' modeling, as previously described, to identify dietary factors that best predict changes in these taxa or clusters. Additionally, we will investigate the tissue and stool microbiome-diet relationship using principal components analysis to identify significant trends among the dietary factors using coinertia analysis. To investigate the microbiome-diet relations during treatment, we will use the microbial clusters and calculate the  $\log_2$  fold change in the clusters from baseline. We will then determine how much the clusters change from baseline according to dichotomous values of macronutrients.

**Microbiome-treatment analysis:** To evaluate differential abundance comparing treatment time points to baseline (prior to surgery and post-surgery/pre-treatment), DESeq2 will be used to control operational taxonomic unit (OTU) over-dispersion between replicates; OTUs will be considered significantly differentially abundant between time points if the false discovery rate (FDR) corrected p-value is below 0.1. A change in relative abundance will be defined as a fold change between mean log relative abundance during treatment phase (week 4, 14, 24) and baseline (prior to surgery). Taxa found to be significantly differentially abundant between treatment time points and baseline (FDR corrected p-value  $<0.05$ ) will be put into an adjusted regression model to control for age, education, income level, marital status, and activity level, diet quality (HEI), tumor stage, medical history with p-values corrected for multiple hypothesis testing using FDR adjustment.

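### The 5% abundance filter discards part of the 0.25–1.0% genera on which the power section focuses, and keeps a rare genus only if at least one sample is extreme

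*Protocol*

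**What the plan says.** The power section (Taxonomic differential abundance analysis) takes its taxa from a public colorectal cancer stool data set: "we identified 92 genus-level groups that each represented (on average) at least 0.25% of sequences from the CRC or healthy patient groups". It then narrows the emphasis: "here we focus on power results for organisms reflecting an average of 0.25-1.0% of 16S sequences in the gut microbiome", with the reason that "detecting differences in these rare taxa may be critical to our study". The power table gives this band its own rows. For a 200% relative increase with 40 versus 100 individuals the stated power is 92.3%. Genera above 1% have separate rows.

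The bioinformatics overview in section 4.3 sets the analysis filter: "taxa with <5% abundance in all samples will be dropped from downstream analysis". It is placed before the diversity metrics and the differential abundance work in R. The taxonomic rank at which 5% applies is not given. The pipeline builds 99% OTUs, and the Microbiome-treatment analysis in section 4.4 works at that level: "DESeq2 will be used to control operational taxonomic unit (OTU) over-dispersion between replicates".

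On the number of samples, the sample size paragraph says "we need to collect at least 560 stool samples from 112 people".

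**The concern.** The filter threshold is 5 times the top of the emphasised band (5 / 1.0) and 20 times its bottom (5 / 0.25). Under the literal wording a taxon is dropped if it never reaches 5% in any sample, so each rare taxon's fate rests on its single largest value. This has two consequences.

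- Some of the genera that the plan singled out never reach the analysis, and the tabulated power does not apply to them.
- At a given mean, the rule keeps variable genera and drops stable ones. Stable genera are those for which the planned t-test has the most power.

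The part of Aim 1 that links taxa to treatment and to chemotherapy-induced diarrhea (CID) is affected. Richness-type alpha diversity is also truncated; weighted UniFrac is affected less. Measured metabolites, circulating cytokines, dietary intake and the CID endpoint itself do not pass through the filter.

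**Working it through.** **Inputs from the protocol.** Filter at 5%; band of means 0.25–1.0%; 16 power values for that band (relative differences of 50, 100, 200 and 300%; 20, 40, 50 and 75 versus 100); alpha 0.05, taken as two-sided; 112 people. Sample numbers: 560 as stated (5 per person), or 112 × 8 = 896 if the collection schedule is counted (one before colonoscopy, one before treatment, two at each of three chemotherapy visits).

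**Assumptions.** The protocol gives no standard deviations, so the coefficient of variation (CV = SD/mean) has to be inferred from the power table. Means are taken as uniform over the band, abundances as lognormal or gamma, and samples as independent.

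**Step 1: the plan's own power figure.** For a relative increase r, the standardised difference is d = r / CV. A power of 92.3% at 40 versus 100 needs d = 0.638, so CV = 2 / 0.638 ≈ 3.1. One CV does not fit the whole band: back-solving the 16 cells gives values from 1.8 to 4.4. That pattern is what averaging power over genera with different variances would produce. A lognormal spread of CVs with median about 2.14 and log-SD 0.51 reproduces all 16 cells to within about 1.2 points, and gives 93.0% where the table has 92.3%.

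**Step 2: probability that a genus is dropped.** P(dropped) = F(5%)^N, where F is the distribution function of one sample's abundance and N the number of samples.

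Worked case: mean 0.5%, CV 2, lognormal, N = 560.

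- Log-variance = ln(1 + 2²) = 1.609, log-SD = 1.269.
- z = (ln(5/0.5) + 1.609/2) / 1.269 = (2.303 + 0.805) / 1.269 = 2.449, so F = 0.9928.
- 0.9928^560 ≈ 0.018.

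The same mean and N at other CVs:

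| CV | lognormal | gamma |
|---|---|---|
| 1.0 | 66% | 98% |
| 1.5 | 11% | 27% |
| 2.0 | 2% | 1% |
| 3.0 | 0.2% | about 0 |

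This is the selection effect: the more stable the genus, the more likely it is to be lost.

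**Step 3: averaged over the fitted CVs.** Share dropped, lognormal / gamma:

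| Mean abundance | N = 112 | N = 560 | N = 896 |
|---|---|---|---|
| 0.25% | 82% / 78% | 46% / 55% | 36% / 49% |
| 0.5% | 47% / 41% | 13% / 20% | 9% / 17% |
| 1.0% | 10% / 8% | 1% / 3% | 1% / 2% |
| Whole band | 38% / 33% | 12% / 17% | 8–9% / 15% |

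If means are log-uniform instead, the whole-band loss is 47% / 42%, 17% / 23% and 12% / 20%. At means of 2% and 3%, using CVs fitted to the rows above 1% (median 1.32, log-SD 0.45), the loss is at most 1.4% and about zero.

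N = 112 treats all samples of one person as a single sample. Within-person correlation puts the effective number somewhere between 112 and the number collected.

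**Step 4: which genera remain.** Dropped genera have a median CV of about 1.0–1.6, kept ones about 2.2–2.6.

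**Step 5: kept and detected.** For a 200% increase, let 40/140 of samples sit at three times the mean with equal SD, and average t-test power × P(kept). The probability that a genus is both kept and detected is 61–62% at N = 112, 75–80% at N = 560 and 78–84% at N = 896. Among kept genera, power is still about 90–92%, so nearly all of the drop comes from removal.

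**The case against.** The strongest reply is that the size of the loss is inferred. No standard deviations are given, the CV spread is fitted to a table on the premise that each cell averages over genera, and the 33–38% figure needs all samples of one person to be redundant. At the planned 560 samples the loss is 12–17%. If control stool from people without stage II/III disease or tissue samples also count, N rises further; at an assumed 1,500 the loss is 6–13%. This stands: the figures are illustrative, and the 560-sample range is the one to lead with.

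It is also true that the table remains nearly right for the genera that are kept, that the loss falls mainly at the lower end of the band, and that the protocol never claimed a kept-and-detected probability. The 92.3% is not shown to be wrong.

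A second reply is that a prevalence rule was meant, dropping taxa present in fewer than 5% of samples. The conflict would then largely disappear. But the text says abundance, so that intention would itself need a correction. A mean-abundance reading is worse, since it removes the whole band.

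A third is that the sentence opens by referring to diversity analyses, so it might not bind the differential abundance work. The sentence goes on to drop the taxa from downstream analysis without limit, and no second filter is given for differential abundance.

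**Conclusion.** The concern holds: the rule is wrong as written. The conflict between a 5% filter and a 0.25% floor with emphasis on 0.25–1.0% is in the text and needs no modelling, nor does the dependence of each rare genus on its largest sample.

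The size does rest on assumptions. With CVs inferred from the power table, lognormal or gamma abundances, uniform means and 560 independent samples, 12–17% of the band is lost; the range is about 8–15% at 896 samples and 33–38% at an effective 112. The protocol does not say how many of the 92 genera lie in the band, so the loss cannot be given as a count.

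These are genus-level figures. If the filter acts on OTUs, the loss is larger, because no OTU can be more abundant than the genus that contains it. This should be fixed before analysis, but it does not touch the CID endpoint or the measured metabolites and cytokines.

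**What to change.** Replace the 5% rule with one that agrees with the power section, and state its unit and taxonomic rank. One option is a mean relative abundance of at least 0.25% at genus level. If a share of samples was intended, write it as a prevalence rule. If OTUs are tested with DESeq2, give the OTU cut-off separately. Say that alpha and beta diversity are computed before this filter.

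The cost is one or two lines of protocol and pipeline text before analysis, with no new data or samples. The downside is that more taxa enter the false-discovery-rate correction, which lowers power somewhat for each.

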### 3. Objectives & Specific Aims

**Objective:** This is a formative study to lay the groundwork for establishing a large cohort of incident colon cancer to examine the microbiome-immune relationship in colon cancer outcome. Our hypothesis is that colon cancer treatment, recurrence and survival are compromised by treatment-induced dysbiosis and dependent upon pre-treatment microbial structure. We plan to address this hypothesis with the following aims:

**Aim 1: Determine if the gut microbiome and microbial metabolites are altered in response to cancer treatment and correlate with CID incidence and severity in stage II/III colon cancer**

Sub-Aim1a: Quantify the gut microbiota prior to surgery and treatment, and at 3 time points during FOLFOX, and correlate with CID incidence and severity

Sub-Aim1b: Quantify microbial pathway abundance and fecal metabolite levels prior to, and during treatment, and determine their associations with incidence and severity of CID

Sub-Aim1c: Quantify circulating and tumor tissue cytokine levels prior to, and during treatment, and determine their associations with the gut microbiota, and incidence and severity of CID

**Aim 2: Determine if the dietary history or dietar intake during treatment is associated with CID incidence and severity in stage II/III colon cancer**

Primary outcomes: CID incidence and severity and gut microbiome and metabolome changes. The patients with colon cancer, serving as their own controls, will provide stool samples that enable clinicians to predict toxicity of anti-cancer therapy in stage II/III colon cancer patients.

Secondary outcomes: Circulating cytokines, dietary history and changes during treatment, stool index changes

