##### **Study procedures:**

This study will collect two sets of data from subjects at baseline (pre-treatment) and on-treatment, as outlined in the Study Design section above.

After specimen collection and coding, microbial DNA will be isolated from the microbiome specimens and fecal metabolites identified. The DNA will be used to conduct DNA sequencing (metagenomics) in accordance with existing protocols through the Integrated Human Microbiome Project (iHMP) study of IBD. The fecal metabolites will be used to produce spectral profiles for quantification using protocols from the iHMP. RNA will be isolated from tissue samples and separate section preserved in Carnoy's to determine biofilm formation. RNA will be used to conduct gene expression assays to confirm taxa identified from sequencing, and blood samples will be used to conduct cytokine assay.

In compliance with BSW protocols, subjects will be screened after consent to verify eligibility. No interventions, device or drugs will be used as part of this observational study. Each participant will serve as his or her own control for the observational (and large cohort) study since this is a prospective cohort design, thus no randomization procedures will be employed. In addition, the questions being asked (e.g. whether the stool microbiome is predictive of treatment toxicity) are dependent upon the participant's baseline data.

This study will consist of potentially five study visits as described below.

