**The third through fifth study visits** (1 hour each) will take place on the 2nd(TD 15), 6th (TD 71) and 10th (TD 128) rounds of IV chemo of treatment (i.e. chemotherapy) at the BSWH center at which they are having their treatment. During this study visit, 2 blood vial samples will be taken as part of the routine clinical visit and the patient will be given two additional stool sample kits to take home to collect stool on the day before chemo starts and before chemo begins and the 2nd day and after their chemotherapy round is complete (i.e. if the infusion starts on Monday, the subject collect a stool sample on that Friday). After

each study visit, the patient will produce 2 stool samples (day before chemo starts and on the 2nd day after their chemo round ends) and drop it off at their treatment hospital or mail (FedEx) it into to the sequencing center at Baylor University. Again, they will be asked to complete the online 24 hour dietary recall (**ASA24**) at home within 72 hours of producing the stool samples. This is the same procedure that will be followed in the fourth and fifth study visits. During each of these visits, the REA or GI physician will ask about incidence and severity of chemotherapy induced diarrhea (**CTCAE – Gastrointestinal/Diarrhea, Grade 1-5**).

The REA will either call the subject or send a text message (if subject agrees) through Twillo after each visit to remind the subject of the days that stool collection and 24 hour (ASA24) recalls should occur.

The REA will obtain interval information from the participant according to the protocol and will provide subjects with stipends for each stool collection provided, which will include \$20 for each specimen collected (stool) up to \$160. If the patient was unable to provide a stool sample at the designated time point due to treatment side-effects they will still be given the compensation for completing the study. Thus, if patients complete all sample collections and all follow up visits, they may receive up to \$160.

Only [name] and the REA will have access to the data-collection sheets and registration forms that will be kept in a locked cabinet at the clinical site.

**Primary data endpoint:** At the end of the observational study we will assess incidence, duration and severity of chemotherapy-induced diarrhea.

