**Secondary data endpoints:** The secondary outcomes will include other side effects, including oral mucositis and constipation, circulating cytokine levels, fecal/tissue/blood metabolites, nutrient intake, and changes in microbiome from baseline.

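### The protocol names an unpaired Mann-Whitney test for time-point comparisons within the same patients; it does not fit the design and, in the usual case, loses power for small shifts

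*Protocol*

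**What the plan says.** Protocol section 4.3, Data Collection, Bioinformatics overview: "Mann-Whitney tests corrected for multiple testing (Benjamini–Hochberg (FDR)) will be used to conduct initial comparisons between time points".

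The design is within-patient. Section 3 describes "The patients with colon cancer, serving as their own controls", and section 4.3, Study procedures, says "Each participant will serve as his or her own control for the observational (and large cohort) study".

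Other analyses in section 4.4 allow for repetition. Linear mixed models for repeated measurements are named for community state types and for cytokines, and an adjusted mixed model for metabolites. For individual OTUs across time points, the Microbiome-treatment analysis names DESeq2.

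The number of stools per treatment time point is not settled. For visits three to five, section 4.3 says "the patient will produce 2 stool samples (day before chemo starts", with the second on the second day after the round. The Stool microbiome paragraph lists one, on the second "day after TD15, TD71 and TD128". The sample-size text says "we need to collect at least 560 stool samples from 112 people".

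**The concern.** Mann-Whitney takes its standard error from two independent groups. When the same patients are measured twice and their values correlate positively, the difference between time points varies less than that standard error assumes. The test then rejects too rarely, and small within-patient shifts are missed. A design that uses patients as their own controls gives up its main advantage in this step.

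At stake is the first screen of microbiome change. Section 3 lists that change among the primary outcomes. Section 4.3 instead gives as the primary data endpoint "we will assess incidence, duration and severity of chemotherapy-induced diarrhea" and puts "nutrient intake, and changes in microbiome from baseline" among the secondary ones.

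Naming a test that does not fit the design is different from leaving a detail to the SAP: here the protocol has made the choice.

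**Working it through.** **Inputs.** At least 100 patients for differential abundance and 112 to be recruited (Sample size); alpha 0.05, taken as two-sided (Taxonomic differential abundance analysis). The within-patient correlation r is not in the protocol; 0.1 to 0.7 is assumed.

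**Effect scale from the protocol's power table.** The protocol gives 92.3% power for 40 vs 100 individuals and a 200% increase in genera at 0.25-1.0%. Solving the two-sample t-test power for the standardised difference gives 0.64 SD. In the same column, 67.2% (100% increase) gives 0.45 SD and 30.6% (50% increase) gives 0.27 SD. These scales are approximate: a single 0.638 SD gives 73.3%, 92.3%, 95.5% and 98.6% across the four columns, against the stated 84.6%, 92.3%, 93.9% and 96.0%. That pattern would fit averaging over genera with different variances and does not show an error.

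**Size, normal approximation.** The unpaired standard error is SE = sqrt(2/n), in SD units. The true standard error of the within-patient difference is SE × sqrt(1 − r). So the true size is 2Φ(−1.96 / sqrt(1 − r)):
- r = 0.1: 2Φ(−2.07) = 3.9%
- r = 0.3: 2Φ(−2.34) = 1.9%
- r = 0.5: 2Φ(−2.77) = 0.6%
- r = 0.7: 2Φ(−3.58) = 0.03%
- r = −0.3: 2Φ(−1.72) = 8.6%

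**Power, normal approximation, n = 100, shift 0.27 SD, r = 0.5.** SE = 0.1414 and 0.27 / 0.1414 = 1.909.
- Unpaired: Φ((1.909 − 1.96) / 0.707) = Φ(−0.07) = 47%.
- Paired: Φ(1.909 / 0.707 − 1.96) = Φ(0.74) = 77%.

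**Simulation of the actual rank tests** (bivariate normal pairs, n = 100, 10,000 data sets per cell, two-sided 5%). Power is Mann-Whitney vs signed-rank:

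| r | Size of Mann-Whitney | 0.27 SD | 0.45 SD | 0.64 SD |
|---|---|---|---|---|
| 0.1 | 3.8% | 45 vs 49% | 88 vs 89% | both over 99% |
| 0.3 | 2.1% | 45 vs 60% | 91 vs 96% | both over 99% |
| 0.5 | 0.8% | 45 vs 74% | 94 vs 99% | both 100% |
| 0.7 | 0.1% | 43 vs 92% | 98 vs 100% | both 100% |

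Signed-rank size stays at 4.8% to 5.1%. At r = −0.3 the Mann-Whitney size is 8.5%. Lognormal data with n = 112 give the same direction: at 0.2 SD and r = 0.5, 24% vs 47%.

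**Stools per time point.** The visit schedule gives 1 + 1 + 3 × 2 = 8 stools per patient, as does the stipend (160 / 20 = 8). The sample-size text gives 560 / 112 = 5. If two stools per visit were entered as independent values and correlated more strongly within a visit than between visits, the size could exceed 5%. For two visits with two stools each it is 10.9% at between-visit 0.1 and within-visit 0.7, but 2.3% at 0.5 and 0.7.

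**Missing samples.** With 20% of samples missing at random per time point, n = 112, r = 0.1 and 0.3 SD, signed-rank on complete pairs has about 44-46% power, against 50% for Mann-Whitney on all available samples.

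**The case against.** The strongest reply is that this is an initial comparison. No later step is said to take its result, DESeq2 declares the OTUs, and mixed models handle several of the other repeated outcomes. The error is in the conservative direction, in a study that calls itself formative. The clearest loss sits at 0.27 SD, the 50% row for rare genera, where the protocol's own table shows only 20.5% to 40.6% power. The protocol also plans to drop taxa below 5% abundance in all samples, which may remove many rare genera. All of this stands and limits the weight of the point. It does not make the named test right. For genera above 1%, the 50% row corresponds to about 0.37-0.42 SD, and a loss remains there: 75 vs 78% at correlation 0.1 and 79 vs 95% at 0.5.

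A second reply is that normal, complete data flatter the paired test. This also stands. With lognormal data, 30% zeros and 20% missing (all assumed), at 0.45 SD Mann-Whitney has about 79-80% against 64-68% for signed-rank at correlation 0.1, and 80-82% against 75-79% at 0.3. A blanket switch to signed-rank would therefore be poor advice.

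Three stronger readings are tempting:
- *The test inflates false positives.* Through dependence this needs negative within-patient correlation, or the stools of a visit pooled as independent. The protocol states neither.
- *Most changed taxa would be missed after the FDR correction.* Such counts need an assumed number of shifted taxa. The sentence also does not say whether it concerns taxa, diversity or both.
- *The later taxon analysis has the same fault because DESeq2 states no patient term.* That is model specification commonly left to the SAP, which is not at hand. The two FDR cut-offs in that paragraph (0.1 and 0.05) are a separate matter.

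**Conclusion.** The point holds in limited form. The protocol fixes an independent-groups test for samples from the same patients, and no text pairs it. The mismatch itself needs no assumption.

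The size of the consequence does. It rests on one stool per patient per time point, complete and roughly normal data, and a positive correlation of 0.1 to 0.7. On those terms the test is conservative (true size about 4% down to 0.1%). At 0.27 SD with 100 patients it has about 45% power, against 49% to 92% for a paired test. At the scale of the highlighted 200% increase nothing is lost, so a reader should not infer that the protocol's power target is undermined. The change is worth making before analysis, but it does not threaten the study.

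**What to change.** In the Bioinformatics overview, replace Mann-Whitney for time-point comparisons with a mixed model with a patient random effect on suitably transformed values, as section 4.4 already plans for community state types. This keeps patients with incomplete samples and can use every stool. If few pairs are incomplete, a Wilcoxon signed-rank test on within-patient differences is an alternative, provided the text states which stool, or the patient's visit mean, represents each time point. Keep Benjamini-Hochberg. The Mann-Whitney tests by Healthy Eating Index at baseline compare different patients and can stay.

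The cost is wording and code, with no extra patients or samples. The downsides are that the mixed model needs a transformation that copes with skew and zeros, and that signed-rank drops incomplete pairs and can fall below Mann-Whitney when correlation is low and samples are missing.
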